10.1. Sample Size Determination

Approximately 72 subjects will be enrolled so that approximately 60 healthy volunteers complete this study. This study is designed to test noninferiority (NI) of lasmiditan relative to placebo, with a diphenhydramine test versus placebo to confirm the sensitivity of the simulator to detect treatment effects. The following assumptions were made in the sample size computation: (a) SD of differences between lasmiditan and placebo within subject for SDLP is approximately 9.5 cm; (b) the true difference between lasmiditan doses and placebo is 0; and (c) the NI margin is proposed to be 4.4 cm, which is the effect seen with 0.05% of BAC. Under these assumptions, a sample of 60 subjects would provide >90% power to establish NI of either dose of lasmiditan compared to placebo in terms of the primary end point, SDLP. This sample size is more than adequate to detect diphenhydramine differences, which are anticipated to exceed the NI margin, from placebo.

Subjects who are randomized but who do not complete all 4 periods during the Treatment Phase may be replaced. Replacement subjects will enter the same treatment sequence as the original subjects to complete all 4 periods.

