10.3.3. Pharmacodynamic Analyses

The primary endpoint, SDLP, will be analyzed using a mixed model with fixed effects for sequence, period, and treatment, and a random effect for subject within sequence for each of the driving time points. Separate models will be used for each of the driving time points.

Secondary endpoints will be evaluated similarly; however, Lane Exceedance will be log transformed (more specifically, $\ln[x+1]$) prior to analyses. Pairwise comparisons for readiness to drive will be analyzed using McNemar test.

For the primary and secondary endpoints, pairwise comparisons (hypothesis tests) of differences in means, and 95% confidence intervals on differences will be provided at each time point for

1. Lasmiditan 100 mg versus placebo
2. Lasmiditan 200 mg versus placebo
3. Diphenhydramine 50 mg versus placebo

In addition, pairwise within-subject differences in SDLP greater than 4.4 cm in absolute value (equal to the previously found difference between placebo and 0.05% BAC for the CRCDS) will be compared using McNemar test. Furthermore, these pairwise, within-subject differences in SDLP will be tested for symmetry about zero using the maximally selected McNemar test.

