9.4.2 Pharmacodynamic Statistical Methodology

The primary endpoint, SDLP, will be analyzed using a mixed repeated measures model with fixed effects for sequence, period, and treatment, with repeated observations for subjects for each of the driving time points. An unstructured covariance structure and Kenward-Roger degrees of freedom will be used. In the event an unstructured covariance structure fails to converge, a variance components covariance structure will be assumed. Separate models will be used for each of the driving time points. In addition to assessments of treatment effect, p-values for significance testing of period and sequence effects will be provided.

All secondary endpoints (excluding total collisions and self-reported readiness) will be analyzed for each of the time points using a mixed repeated measures model similar to the one used for the primary analysis, with sequence, period, and treatment as fixed effects, with repeated observations for subject. Separate models will be used for each of the driving and cognition time points. Lane Exceedance will be log transformed as $\ln[x+1]$ prior to analyses.

For the primary and secondary endpoints (excluding total collisions and self-reported readiness), pairwise comparisons of differences in means and the corresponding 95% confidence intervals (CIs) of the differences will be provided at each time point for:

- Lasmiditan 100 mg versus placebo
- Lasmiditan 200 mg versus placebo
- Diphenhydramine 50 mg versus placebo

Example SAS code (mixed model for primary and secondary endpoints, including with data sorted for each endpoint as follows):

```
proc sort data=adxx; by atptn usubjid aperiod; run;

proc mixed data=adxx alpha=0.05;
  by atptn;
  class trtpn aperiod trtseqp usubjid ;
  model aval = aperiod trtpn trtseqp / ddfm=kr;
  repeated / sub=usubjid type=un;
  lsmeans trtpn / cl pdiff alpha=0.05;
  estimate '100 vs. Pbo' trtpn -1 1 0 0 / cl alpha=0.05;
  estimate '200 vs. Pbo' trtpn -1 0 1 0 / cl alpha=0.05;
  estimate 'Dip vs. Pbo' trtpn -1 0 0 1 / cl alpha=0.05;
run;
```

In addition, pair-wise within-subject differences in SDLP greater than 4.4 cm in absolute value (equal to the previously found difference between placebo and 0.05% BAC for the CRCDS) will be compared using McNemar's test. Pair-wise, within subject differences in SDLP will also be tested for symmetry about zero (Laska 2012) using the maximally selected McNemar test).

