9.4.3 Adjustments for Multiplicity

To address multiplicity of testing associated with 2 doses of lasmiditan versus placebo at 3 time points for the primary endpoint of SDLP, ascending doses of lasmiditan at descending time points will be interpreted in a sequential manner, starting with the 100-mg dose at 24 hours and proceeding to the 200-mg dose and earlier time points via a graphical multiple comparisons procedure, as given in the following figure (Figure LAIF 3). The value of w , the split of alpha after testing 100 mg at 24 hours, will be set to 0.95 (i.e., propagating 95% of alpha to the 100 mg 12 h end point and 5% of the alpha to the 200 mg 24 h end point, assuming the 100 mg 24 h end point is successful).

[figure not shown]

Figure LAIF.3 Pharmacodynamic statistical inference – graphical multiple comparisons procedure.

Doses of lasmiditan will be considered non-inferior to placebo at a time point if the upper 95% CI on the difference in SDLP between that dose and placebo is less than 4.4 cm.

No adjustment to alpha levels will be made for the comparison of diphenhydramine either to placebo or to lasmiditan, or for secondary endpoints or analyses. Strong control of Type I error for non-inferiority, for the primary endpoint will be at the 0.05 alpha-level (two-sided).

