11. CHANGES FROM THE PROTOCOL SPECIFIED STATISTICAL ANALYSES

The mixed model specification was updated to use a REPEATED statement rather than a RANDOM statement in the SAS[®] MIXED procedure, to more readily allow for the estimation of an unstructured covariance matrix. Additional details regarding model specification and outputs are also provided in Section 9.4.2.

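### SAP 9.4.2 leaves the index of the unstructured covariance unstated; the example code orders it by period record, so each lasmiditan–placebo limit uses a standard error pooled over all four arms

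*SAP*

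**What the plan says.** - SAP 9.4.2 on the primary model: "An unstructured covariance structure and Kenward-Roger degrees of freedom will be used". One model is fitted per driving time point, with sequence, period and treatment as fixed effects. The text does not say whether the rows of the matrix are periods or treatments.
- The example code sorts the data with "proc sort data=adxx; by atptn usubjid aperiod; run" and specifies the covariance as "repeated / sub=usubjid type=un". No effect stands between the keyword and the slash.
- SAP 11 explains the move from a RANDOM to a REPEATED statement: "to more readily allow for the estimation of an unstructured covariance matrix". It is also silent on the index.
- Protocol 10.3.3 had specified "a random effect for subject within sequence for each of the driving time points".
- SAP 9.4.3: a dose is "considered non-inferior to placebo at a time point if the upper 95% CI on the difference in SDLP between that dose and placebo" is below 4.4 cm. Testing runs in order, "starting with the 100-mg dose at 24 hours and proceeding to the 200-mg dose and earlier time points".
- Protocol 10.1 gives one variability figure: "SD of differences between lasmiditan and placebo within subject for SDLP is approximately 9.5 cm". No SD or covariance is given for any single arm.

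**The concern.** A programmer working from the text alone could index the matrix by treatment. One who copies the code would index it by period. The two give different confidence limits for the same primary comparison.

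Under the code's index, every treatment occurs once in each period, so each period variance averages all four treatments. The lasmiditan–placebo SE then borrows from diphenhydramine and from the other dose. If those arms vary differently, the upper limit compared with 4.4 cm is too wide or too narrow. Too wide costs power at 100 mg 24 h, on which the rest of the testing sequence depends. Too narrow raises the chance of declaring a dose noninferior when it is not, although SAP 9.4.3 claims strong Type I error control.

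There is a second, plainer problem. With no repeated effect named, a subject whose earlier-period record is absent from the dataset has later records placed in the wrong row. Dropout after a completed period does not cause this; a gap does.

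**Working it through.** **Inputs.** SD of the within-subject difference 9.5 cm, true difference 0, margin 4.4 cm, 60 completers (Protocol 10.1, SAP 7); two-sided 95% limit (SAP 9.4.3); the four sequences of Table LAIF.3. The arm SD multipliers below are assumptions.

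**1. The plan's own figure.** SE = 9.5/√60 = 1.226 cm. Power = Φ(4.4/1.226 − 1.96) = 94.8% (94.2% with the t distribution). The stated figure of more than 90% reproduces.

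**2. What the period index pools.** In large samples the period-indexed matrix tends to the average of the four treatment covariance matrices, each permuted by its sequence. In Table LAIF.3, placebo and 200 mg always occupy periods 1 and 4 or periods 2 and 3, and so do 100 mg and diphenhydramine. The model variance for 200 mg versus placebo is therefore built on

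½[Var(200 mg − placebo) + Var(100 mg − diphenhydramine)],

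and the limit is calibrated when this equals Var(200 mg − placebo).

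**3. Equal between-arm covariances** (for example a random subject intercept). For either dose the condition reduces to

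model SE / true SE = √[2 × mean of the four arm variances / (placebo variance + dose variance)],

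where the variances are within-subject.
- Diphenhydramine SD × m: ratio = √[(3 + m²)/4].
- 200 mg SD × m, contrast 200 mg versus placebo: ratio = √[(3 + m²)/(2(1 + m²))].
- One-sided false noninferiority = Φ(−1.96 × ratio). Power in the diphenhydramine rows = Φ(4.4/1.226 − 1.96 × ratio).

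| Assumed pattern | Contrast | SE ratio | False noninferiority | Power |
|---|---|---|---|---|
| Equal variances | either dose | 1.00 | 2.5% | 94.8% |
| Diphenhydramine × 1.25 | either dose | 1.068 | 1.8% | 93% |
| Diphenhydramine × 1.5 | either dose | 1.146 | 1.2% | 91% |
| Diphenhydramine × 2 | either dose | 1.323 | 0.5% | 84% |
| 200 mg only × 1.25 | 200 mg | 0.944 | 3.2% | – |
| 200 mg only × 1.5 | 200 mg | 0.899 | 3.9% | – |
| Both lasmiditan doses × 1.5 | either dose | 1.00 | 2.5% | – |

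**4. Unequal covariances.** Comparing arm variances alone is then not enough. Both cases concern 200 mg versus placebo.
- All variances 90, placebo–200 mg covariance 30, other covariances 45. Var(200 mg − placebo) = 180 − 60 = 120 and Var(100 mg − diphenhydramine) = 180 − 90 = 90, so the pooled value is 105. Ratio = √(105/120) = 0.935; false noninferiority 3.3% although the arm variances are equal.
- Diphenhydramine variance 135 and its covariances 67.5, others 90 and 45. Both differences have variance 90 (90 + 135 − 135 = 90), so the ratio is 1.00 although the arm variances differ.

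**5. Simulation of the SAP model** (REML, Kenward–Roger, 15 subjects per sequence, within-subject SD 9.5/√2 = 6.72, 12,000 replicates). Power at 100 mg, period index against treatment index:
- equal variances: 93.5% against 93.9%
- diphenhydramine × 1.25: 92.0% against 94.2%
- diphenhydramine × 1.5: 89.4% against 94.3%
- diphenhydramine × 2: 80.8% against 93.9%

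The period index still gives 90.6% at × 1.4. With 72 enrolled and the partial data of 12 dropouts kept (4,000 replicates), the three diphenhydramine patterns give 93.3% against 95.2%, 91.1% against 95.1%, and 84.0% against 95.1%. With 200 mg alone × 1.25 or × 1.5, false noninferiority is 3.3–3.5% or 3.7–3.9% under the period index, against 2.7% or 2.3–2.4% under the treatment index.

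**The case against.** **Pooling is not new in the SAP.** This stands. The protocol's random-subject model pools in the same way: simulated power is 93.1%, 90.7% and 83.0% at diphenhydramine × 1.25, × 1.5 and × 2. SAP 11 promises an unstructured matrix, not arm-specific standard errors.

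**The anti-conservative case is the less likely one.** This largely stands. It needs 200 mg to be more variable while diphenhydramine is not. If SDs rise in the order placebo, 100 mg, 200 mg, diphenhydramine, then with equal covariances both lasmiditan limits are exact or conservative. The half-life of about 4 h in Protocol 3.2 makes excess variability from 200 mg hard to argue at 24 h (24/4 = 6 half-lives), less so at 8 h (2 half-lives). But diphenhydramine being the most variable arm is also an assumption: Protocol 5.4 and SAP 7 concern its timing and mean effect, not its variance.

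**The power loss is modest.** This stands up to about × 1.4 with 60 completers, and somewhat further when partial data are kept.

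**The remedy is a trade-off.** There is a price, but the risks are not symmetric. With complete balanced data the treatment index stayed calibrated whether variance differed by treatment or by period. The period index did not.

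**Conclusion.** The concern holds as a gap in specification with a conditional consequence. The SAP text does not fix the covariance index. The code makes it record order, hence period when no earlier record is absent, and each noninferiority limit then rests on a four-arm pooled SE. Calibration requires the pair's difference variance to match the pooled one. Comparing the pair's mean variance with the four-arm mean is the right test only if between-arm covariances are equal.

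Three stronger readings are tempting and are not supported.
- A reader might infer that the primary model is invalid or the Type I error inflated. The model is valid under equal arm variances and covariances, and no document shows that they are unequal.
- A reader might infer that the planned power is wrong. It reproduces, and no stated figure is contradicted.
- A reader might infer that the treatment SDs promised in SAP 9.4.2 settle the matter. They would reveal unequal arms, but no rule links them to the noninferiority limit.

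Every multiplier above is assumed. The change should be made, but the analysis does not fail without it.

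**What to change.** In SAP 9.4.2, change the code to `repeated trtpn / subject=usubjid type=un;`, keep `aperiod` as a fixed effect, and apply the same change to the secondary mixed models. State in the text, not only in example code, that the covariance is unstructured across treatments within each time point. Naming the effect also removes the misplaced-row problem.

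If the sponsor prefers to keep the period index, the minimum is to name `aperiod` as the repeated effect, state that a common variance structure across arms is assumed, and add the treatment-indexed fit as a sensitivity analysis.

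Cost: one word of code and one sentence. Kenward–Roger degrees of freedom fall from about 113–148 to about 57. Under equal variances power is essentially unchanged. If variance differs by period rather than by treatment, about 2–3 power points are lost (Period 1 SD × 1.5: 87.4% against 89.5%), with standard errors calibrated under both indexes.

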9.4.3 Adjustments for Multiplicity

To address multiplicity of testing associated with 2 doses of lasmiditan versus placebo at 3 time points for the primary endpoint of SDLP, ascending doses of lasmiditan at descending time points will be interpreted in a sequential manner, starting with the 100-mg dose at 24 hours and proceeding to the 200-mg dose and earlier time points via a graphical multiple comparisons procedure, as given in the following figure (Figure LAIF 3). The value of w , the split of alpha after testing 100 mg at 24 hours, will be set to 0.95 (i.e., propagating 95% of alpha to the 100 mg 12 h end point and 5% of the alpha to the 200 mg 24 h end point, assuming the 100 mg 24 h end point is successful).

[figure not shown]

Figure LAIF.3 Pharmacodynamic statistical inference – graphical multiple comparisons procedure.

Doses of lasmiditan will be considered non-inferior to placebo at a time point if the upper 95% CI on the difference in SDLP between that dose and placebo is less than 4.4 cm.

No adjustment to alpha levels will be made for the comparison of diphenhydramine either to placebo or to lasmiditan, or for secondary endpoints or analyses. Strong control of Type I error for non-inferiority, for the primary endpoint will be at the 0.05 alpha-level (two-sided).

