5.4. Scientific Rationale for Study Design

Subjects will enter the CRU on Day -1. For the duration of the 4-period study, subjects will remain in the CRU. Each period will be of 3 days duration. It is anticipated that Study Periods 1, 2, 3, and 4 will commence on Study Days 1, 4, 7, and 10, respectively. For logistical reasons, the interval between periods may be extended by up to 2 days to accommodate site schedules. The minimum washout between periods is 3 days. Cognitive testing and driving simulation will be conducted approximately 8, 12, and 24 hours after Dose 1 on Day 1 of each study period. These driving assessment time points are expected to provide a wide range of responses including reversal of impairment.

The study design incorporates a positive control (diphenhydramine 50 mg) to confirm assay sensitivity. Per the FDA's Evaluating Drug Effects on the Ability to Operate a Motor Vehicle: Guidance for Industry (2017), sedating antihistamines are commonly used to understand the magnitude and duration of impairment. Diphenhydramine is a well-known sedating antihistamine available over the counter in the US and has been shown to have a significant

effect on driving performance (Kay et al. 1997, 2016). Diphenhydramine will be administered no more frequently than every 4 hours per package directions, coinciding with time points 2 hours prior to each driving assessment so that the maximum cognitive and sedative effect of the positive control coincide with the initiation of the driving simulation task.

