10.3.3.1. Pharmacodynamic Statistical Inference

To address multiplicity of testing, 2 doses of lasmiditan versus placebo at 3 time points for the primary endpoint of SDLP, ascending doses of lasmiditan at descending time points will be interpreted in a sequential manner, starting with the 100-mg dose at 24 hours and proceeding to the 200-mg dose and earlier time points via a graphical multiple comparisons procedure ([Figure LAIF.3](#)). The value of w , the split of alpha after testing 100 mg at 24 hours, will be specified in the statistical analysis plan.

[figure not shown]

Figure LAIF.3. Pharmacodynamic statistical inference – graphical multiple comparisons procedure.

Doses of lasmiditan will be considered noninferior to placebo at a time point if the upper 95% confidence limit on the difference in SDLP between that dose and placebo is less than 4.4 cm. No adjustment to alpha levels will be made for the comparison of diphenhydramine either to placebo or to lasmiditan, or for secondary endpoints or analyses. Formal statistical tests (where performed) will be 2-sided with testing at the alpha=0.05 level of significance.

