7. SAMPLE SIZE JUSTIFICATION

Approximately 72 subjects will be enrolled so that approximately 60 healthy volunteers complete this study. This study is designed to test noninferiority (NI) of lasmiditan relative to placebo, with a diphenhydramine test versus placebo to confirm the sensitivity of the simulator to detect treatment effects. The following assumptions were made in the sample size computation: (a) standard deviation (SD) of differences between lasmiditan and placebo within subject for standard deviation of lateral position (SDLP) is approximately 9.5 cm; (b) the true difference between lasmiditan doses and placebo is 0; and (c) the NI margin is proposed to be 4.4 cm, which is the effect seen with 0.05% of blood alcohol count. Under these assumptions, a sample of 60 subjects would provide >90% power to establish NI of either dose of lasmiditan compared to placebo in terms of the primary end point, SDLP. This sample size is more than adequate to detect diphenhydramine differences, which are anticipated to exceed the NI margin, from placebo.

Subjects who are randomized but who do not complete all 4 periods during the Treatment Phase may be replaced. Replacement subjects will enter the same treatment sequence as the original subjects to complete all 4 periods.

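### SAP 9.4.3 gives 200 mg at 24 h a first-pass two-sided alpha of 0.0025 but judges it by a fixed 95% limit; applied literally, strong Type I error control fails

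*SAP*

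**What the plan says.** SAP 9.4.3 controls multiplicity over six primary hypotheses (two lasmiditan doses, three times) with a graphical procedure that starts at 100 mg, 24 h. It fixes w, "the split of alpha after testing 100 mg at 24 hours, will be set to 0.95". After the first success, 95% of alpha goes to 100 mg at 12 h and "5% of the alpha to the 200 mg 24 h end point".

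The decision rule follows: "Doses of lasmiditan will be considered non-inferior to placebo at a time point if the upper 95% CI on the difference in SDLP" falls under 4.4 cm. The section ends with a claim about the whole family: "Strong control of Type I error for non-inferiority, for the primary endpoint will be at the 0.05 alpha-level (two-sided").

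Protocol 10.3.3.1 has the same rule: "Doses of lasmiditan will be considered noninferior to placebo at a time point if the upper 95% confidence limit on the difference in SDLP" must be below 4.4 cm. It adds "Formal statistical tests (where performed) will be 2-sided with testing at the alpha=0.05 level of significance", without excepting tests whose alpha comes from the graph.

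SAP 9.4.2 plans 95% intervals for every contrast, and its example code sets alpha=0.05 throughout. SAP 11 lists no change to the NI rule. SAP 7 states that "a sample of 60 subjects would provide >90% power to establish NI of either dose of lasmiditan".

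**The concern.** The weights of a graphical procedure have effect only if each hypothesis is tested at the alpha it currently holds. SAP 9.4.3 allots unequal alphas to two hypotheses that open together, then gives one confidence level for both. The 95% level is exact for 100 mg at 24 h and nearly right for 100 mg at 12 h. It is far too lenient for 200 mg at 24 h before any alpha is recycled to it.

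NI by dose and time is the trial's answer to its primary objective, how long driving is affected. Two analysts following the same SAP could report different answers for 200 mg at 24 h. The SAP specifies no NI p-value and no adjusted interval. The p-values from the example code test a difference of zero, not 4.4 cm. The 95% limit is thus the only NI criterion written out for the group that analyses SDLP.

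**Working it through.** **Inputs.** From SAP 7: SD of within-subject differences 9.5 cm, 60 completers, margin 4.4 cm, true difference 0. From SAP 9.4.3: overall alpha 0.05 two-sided (0.025 in the NI direction), w = 0.95. Assumed, because the documents give no values: correlation 0.5 between doses at the same time, and 0, 0.3, 0.6 or 0.8 between times.

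**1. The plan's own power.** SE = 9.5/√60 = 1.226 cm. Noncentral t with 59 df at two-sided 0.05 gives 94.2% (normal approximation 94.8%). This reproduces the claim of more than 90%, so that claim matches the full 0.05 level.

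**2. Local alphas after the first success.** 100 mg at 12 h: 0.05 × 0.95 = 0.0475. 200 mg at 24 h: 0.05 × 0.05 = 0.0025.

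**3. Cut-offs.** The largest observed difference that still gives NI is 4.4 − t(59) × SE:

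| Two-sided alpha | CI level | Half-width (cm) | Cut-off (cm) | Power at true difference 0 |
|---|---|---|---|---|
| 0.05 | 95% | 2.454 | 1.946 | 94.2% |
| 0.0475 | 95.25% | 2.482 | 1.918 | 93.9% |
| 0.0025 | 99.75% | 3.874 | 0.526 | 66.5% |

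The power column is per comparison and ignores the requirement that 100 mg at 24 h passes first.

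**4. Type I error, testing order respected.** Take 100 mg at 24 h truly 0, and 100 mg at 12 h and 200 mg at 24 h both truly 4.4 cm. The two successors are open together.
- Bound with graph alphas: 0.02375 + 0.00125 = 0.025 one-sided.
- Bound with 95% limits: 0.025 + 0.025 = 0.05 one-sided.

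Simulation (1,000,000 draws of correlated normal test statistics) for between-time correlations 0/0.3/0.6/0.8:
- 95% limits: 0.0484/0.0486/0.0478/0.0468.
- Graph weights: 0.0239/0.0248/0.0250/0.0247.

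With a common correlation between the statistics instead, the 95% rule gives about 0.047 at 0, 0.046 at 0.5 and 0.035 at 0.9. All exceed 0.025. If only 200 mg at 24 h is at the margin, the 95% rule gives 0.025, with no inflation.

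**5. How often the two rules disagree on 200 mg at 24 h.** This depends on the later edges of Figure LAIF.3, which are not visible. The recycling case assumes that full alpha returns once 100 mg passes at 12 h and 8 h at 0.0475 each.

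| Scenario (all other true differences 0) | Disagreement |
|---|---|
| 100 mg 8 h truly 0, no recycling | about 21% |
| 100 mg 8 h truly 0, assumed recycling | about 2% |
| 100 mg 8 h truly 2.2 cm, assumed recycling | 13–15% |
| 100 mg 8 h truly 4.4 cm, assumed recycling | about 21% |

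**The case against.** The strongest reply is that the graph plainly governs. The section is about adjusting for multiplicity, states an explicit split and claims strong control. It also says alpha is not adjusted for the diphenhydramine and secondary comparisons, which implies that it is adjusted for the primary ones. A graphical procedure tests each node at its own alpha by construction, and the literal reading makes w pointless. This is probably the intent, and control then holds. But the operative sentence, the interval plan and the code all say 95%, and a primary decision rule should not have to be inferred.

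Other points stand in part:
- **The hidden figure.** Figure LAIF.3 might carry node levels. The finding needs only the split stated in the text, and later edges cannot change the first-pass 0.0025.
- **The protocol's alpha sentence and the power claim.** The SAP supersedes the protocol's statistics (SAP 3), and the power wording dates from when w was unset. Both are supporting evidence only. The 66.5% is a first-pass figure: with the assumed recycling and all differences 0, power for 200 mg at 24 h, counting the need to pass 100 mg at 24 h first, is about 89%, against 91% under the 95% rule.
- **An unlikely worst case.** With a half-life near 4 h and roughly linear PK (Protocol 3.2), 200 mg at 24 h should resemble 100 mg at 20 h. Both successors at the margin is then improbable. This bears on materiality, but strong control must hold for every configuration.
- **4.7–4.9% is still below 5%.** A two-sided 0.05 level allows 2.5% in the NI direction, which is also what the upper limit of a 95% interval uses.

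**Conclusion.** The concern holds and must be fixed before analysis. SAP 9.4.3 contains two rules for the same hypothesis, and no visible text says which one decides. Under the graph, family-wise error is at most 2.5% one-sided. Under the literal 95% sentence it reaches 4.7–4.9% in the worst configuration with the main assumed correlations, and about 3.5% at a common correlation of 0.9.

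The practical gap is confined to the 200 mg branch before recycling: a cut-off of 0.53 cm against 1.95 cm at n = 60 and SD 9.5 cm. For 100 mg at 12 h the gap is trivial (1.92 against 1.95 cm).

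Disagreement on 200 mg at 24 h ranges from about 2% to about 21%, depending on the unseen recycling edges and on any residual 100 mg effect at 8 h. Such an effect is plausible, since Protocol 5.4 says "These driving assessment time points are expected to provide a wide range of responses including reversal of impairment", though it gives no size. The contradiction itself rests on no assumption about correlation or recycling.

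**What to change.** In SAP 9.4.3, and to match in Protocol 10.3.3.1, replace the NI sentence with: NI is declared for a hypothesis only if the upper limit of the two-sided 100(1 − alpha_local)% CI is below 4.4 cm, where alpha_local is the alpha the graph assigns at that step, including any recycled alpha.

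Then:
- State the first-pass levels: 95% for 100 mg at 24 h, 95.25% for 100 mg at 12 h, 99.75% for 200 mg at 24 h.
- Except the primary NI tests from the general alpha=0.05 sentence in Protocol 10.3.3.1.
- Add code to SAP 9.4.2 for the primary NI tests at alpha_local, and label the 95% intervals as descriptive.
- In SAP 7, say that the power for either dose was computed at two-sided 0.05, or restate it under the graph.

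The cost is wording and a few ESTIMATE statements, with no change to data collection. The 200 mg tests face a stricter bar than the 95% sentence suggests, but the graph already implies it. SAP 3 requires sign-off before first dosing, so the wording should be settled by then.
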